#### Compliance

The ITT analysis provides the most robust estimate of the *causal* impact of the Reach programme on the primary outcome. This is because the ITT analysis focuses on preserving randomisation and so best ensuring that the only difference between the Reach and the Control groups is group membership (all other differences are random). However, the ITT analysis does not take compliance with the Reach programme into account. In other words,

the ITT analysis captures the causal impact of Reach for YP who are randomised to the Reach programme. To estimate the impact of Reach for YP randomised to the Reach programme and who received the programme as intended (and specified), a compliance analysis will be undertaken. A combination of fidelity and dosage of Reach will be drawn on to construct a compliance variable at the YP level. This will identify a subsample of YP in the Reach intervention group who spent the required amount of time with their YW in which ALL of the core components of Reach were covered. This would be defined as receiving a minimum of 32 sessions with YW, and receiving all core components to be compliant. Detailed information on "time per core component" is being collected by the delivery team which will inform this variable. Associations between fidelity and dosage and outcomes will be undertaken as IPE analyses (see protocol for details on this) whilst the binary compliance variable (1 = compliant, 0 = not compliant) will be used to estimate the Compliers Average Causal Effect (CACE) using an instrumental variable and two stage least squares (2SLS) approach. The CACE analyses will provide the best estimate for the impact of Reach for YP who have received the programme as intended (and specified) in terms of fidelity and dosage. However, because CACE does not preserve randomisation, causal conclusions cannot be drawn from these analyses. The ITT and CACE analyses together provide two perspectives; an estimate of the causal impact of being allocated to receive Reach (ITT) and an estimate of the impact of receiving reach as intended and specified (CACE). This analysis will address a further impact evaluation research question as follows:

**RQ15** What is the Compliance Average Causal Effect for the Reach programme on the primary outcome?

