### Introduction

The Reach Programme is targeted intervention aimed at YP (young people) aged 11-16 in secondary schools (years 7-11) who are at risk of suspension (i.e. they have carried out behaviour in their school that would normally qualify for a suspension) or who are persistently absent from school, have 3 indicators of vulnerability (e.g. looked after, domestic violence or substance misuse in the home) and where there are concerns about future involvement in anti-social behaviour and crime as both a victim or perpetrator. YP are referred to the Reach Programme directly from schools. A team of 10 Youth Workers working across the 12 schools deliver one to one sessions to YP over a period of 6 months, covering a set of core components as follows:

- Relationship Building
- Understanding behaviour
- Social Skills training
- Confidence, Wellbeing and Resilience
- Positive Family, Peer, and Community Relationships
- Identifying and Achieving Aspirations
- Recreational Activity

The Reach evaluation is designed as an efficacy trial with internal pilot. The internal pilot phase of the evaluation is now complete, and the efficacy phase began in January 2024 across the same 12 schools that were recruited for the pilot phase. Whist the sample of 12 schools remains the same, the YP recruited to the efficacy phase are different to those recruited at the pilot phase. Please see the Reach Protocol for a more detailed description of the intervention and associated documents (referral form, Theory of Change and Logic Model).

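### The CACE for RQ15 counts partial receipt as no receipt, so it overstates the full-recipient effect if partial recipients benefit, and the SAP's caveat names a different problem

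*SAP*

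**What the plan says.** The Compliance section of the SAP defines full receipt by two joint conditions: "This would be defined as receiving a minimum of 32 sessions with YW, and receiving all core components to be compliant". It then fixes the form of the exposure: "the binary compliance variable (1 = compliant, 0 = not compliant) will be used to estimate the Compliers Average Causal Effect (CACE"). For the estimator, the same sentence names this method: "using an instrumental variable and two stage least squares (2SLS) approach". The instrument is not named; random allocation is the only evident candidate.

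Two statements on interpretation follow. One is favourable: "The CACE analyses will provide the best estimate for the impact of Reach for YP who have received the programme as intended". The other is restrictive: "because CACE does not preserve randomisation, causal conclusions cannot be drawn from these analyses". Graded dose is handled elsewhere: "Associations between fidelity and dosage and outcomes will be undertaken as IPE analyses", with details left to the protocol. The Introduction says that youth workers "deliver one to one sessions to YP over a period of 6 months" and lists seven core components.

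**The concern.** A Reach participant just below the session threshold, or one well above it who missed a single component, gets the same code as a control who had no sessions. If 6 months is taken as about 26 weeks, 32 sessions is 32/26 ≈ 1.2 per week, so someone seen once a week throughout would be coded 0.

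An instrumental-variable estimate for full recipients needs the exclusion restriction: allocation may change the outcome only by moving a person from 0 to 1 on the exposure. If participants coded 0 benefit from the sessions they attended, that benefit stays in the numerator (the ITT effect) while they are left out of the denominator (the compliant share). Their gain is then credited to the full recipients.

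The caveat does not warn of this. Using allocation as the instrument relies on the randomisation; it avoids comparing self-selected compliers with controls. The caveat would suit a per-protocol comparison. It also sits awkwardly with RQ15, which asks for a causal effect. A reader would be alerted to the wrong weakness and told nothing about the likely direction of error.

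**Working it through.** **Inputs from the SAP.** Binary exposure, 32-session and all-component rule, two-stage least squares (Compliance). N = 600, 24 blocks of 25, ICC 0.13, correlation 0.32, MDES 0.21 (Table 2). The SAP gives no compliance rate, session distribution or CACE figure.

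**The SAP's own figure.** The MDES of 0.21 serves below as an illustrative ITT effect, so it was checked first. With 23 degrees of freedom the SAP's simplified formula is

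MDES = 2 × (t₀.₉₇₅ + t₀.₈₀) × √[(1 − ICC)(1 − r²)/(Jn)].

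With r = 0.32: 2 × (t₀.₉₇₅ + t₀.₈₀) × √(0.87 × 0.8976/600) = 0.211. With r = 0.50 and 0.60 it gives 0.193 and 0.178. All agree with Table 2. The point does not depend on this figure.

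**Assumed quantities.**
- pc: share of the Reach arm meeting the full definition.
- pp: share with some receipt, but less than the full definition.
- k: partial recipients' effect as a fraction of the full-recipient effect D.
- Reach participants with no receipt gain nothing, and controls receive no sessions.

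**Formula.** ITT = D × (pc + k × pp). With one binary instrument, two-stage least squares gives in effect ITT/pc = D × (1 + k × pp/pc). The factor in brackets is the overstatement.

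| pc | pp | k | Factor 1 + k × pp/pc |
|---|---|---|---|
| 0.7 | 0.2 | 0.25 | 1.07 |
| 0.7 | 0.2 | 0.5 | 1.14 |
| 0.5 | 0.4 | 0 | 1.00 |
| 0.5 | 0.4 | 0.25 | 1.20 |
| 0.5 | 0.4 | 0.5 | 1.40 |
| 0.5 | 0.4 | 1 | 1.80 |
| 0.3 | 0.4 | 0.5 | 1.67 |
| 0.3 | 0.4 | 1 | 2.33 |
| 0.5 | 0.4 | −0.25 | 0.80 |

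Over pc 0.3–0.7, pp 0.2–0.4 (with pc + pp no more than 1) and k 0.25–1, the factor runs from 1.07 to 2.33.

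**In effect-size units.** Take ITT = 0.21, pc = 0.5, pp = 0.4, k = 0.5. The planned analysis reports 0.21/0.5 = 0.42. The true full-recipient effect is 0.21/(0.5 + 0.5 × 0.4) = 0.21/0.7 = 0.30. Counting any receipt as exposure gives 0.21/0.9 = 0.23. That is the average over everyone who received something: (0.5 × 0.30 + 0.4 × 0.15)/0.9 = 0.23.

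**Simulation.** With N = 600, 4,000 runs, a true full-recipient effect of −0.30 (lower scores are better), and no blocks or covariates, the mean estimate was −0.30, −0.42 and −0.54 for k = 0, 0.5 and 1 at pc = 0.5, pp = 0.4. At pc = 0.3, pp = 0.4, k = 0.5 it was −0.51. These match the formula. The formula does not involve the sample size, so a larger trial would not remove the bias.

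**The case against.** The strongest reply is that overstatement is conditional. A reader might infer that the threshold necessarily violates exclusion and inflates the result. The SAP does not support that: it has no data on benefit below the threshold. At k = 0 there is no bias, and if partial receipt did harm the estimate would be too small. This stands. What can be said is that some benefit from a run of one-to-one sessions is plausible, and that the plan treats graded benefit as an open question by studying dosage against outcome.

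Second, the size rests wholly on assumed inputs, and the mild end of the range (1.07) is minor. This also stands.

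Third, RQ15 supplements an ITT analysis that the SAP ranks as its most robust causal estimate, and the Compliance section already bars causal conclusions from the CACE. That limits the harm but does not cure the problem: the reason given is wrong, and the favourable wording ("The CACE analyses will provide the best estimate for the impact of Reach for YP who have received the programme as intended") remains.

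Fourth, the dosage associations in the IPE mean that dose is not ignored. True, but associations within the Reach arm do not repair the instrumental-variable estimate.

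Finally, a reader might infer that the 32-session analysis should be dropped. It should not. It addresses the question RQ15 poses, and neither a session count nor any-session receipt captures component coverage.

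**Conclusion.** The concern holds in conditional form. The planned CACE is valid for full recipients only if Reach participants coded 0 gain nothing from partial receipt, and the SAP does not state this assumption. If they gain, the magnitude is overstated by 1 + k × pp/pc: about 1.07 to 2.33 over the assumed ranges, and 1.4 in the central example (0.42 reported against 0.30). The actual size cannot be determined from the SAP.

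The error in the caveat does not depend on k: an instrument based on allocation uses the randomisation, and the doubtful assumption is exclusion.

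Only RQ15 is affected. The headline ITT, the sample size and the other research questions are untouched, so this is a should-fix.

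**What to change.** 1. **Replace the caveat.** Name allocation as the instrument. State that the estimate uses the randomisation and is causal only under the exclusion restriction and monotonicity. Add that exclusion is doubtful for the 32-session/all-components variable, so the result is an upper bound on the magnitude of the effect if partial receipt helps. Remove the best-estimate description.
2. **Keep the 32-session analysis and add two pre-specified ones**, both by two-stage least squares with allocation as the instrument:
   - Receipt of any session as the exposure, for which exclusion is credible. This answers a different question, the average effect of any receipt, and supplements the existing analysis.
   - Number of sessions received (0 for controls) as the exposure. State that the result is a weighted average over the dose range, that reading it per 10 sessions needs approximate linearity, and that it does not capture component coverage.
3. **Report the shares** of the Reach arm with full, partial and no receipt, so that readers can apply the factor above.

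The cost is a few sentences in the SAP and two further model runs. Session counts are already needed to build the 32-session variable. The definition of full receipt and the delivery of the programme do not change. The additions should be fixed before the RQ15 results are seen, so that no exposure definition is chosen on its result.

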#### Intra-cluster correlations (ICCs)

For the primary outcome measure and corresponding baseline measure (teacher report SDQ externalising score), ICCs at the school level will be estimated using the 'estat icc' command in Stata. In the analysis section, a table will be included that presents the variance decomposition for the two levels, school and pupil, along with the ICC estimates.

#### **Presentation of outcomes**

Effect sizes will be calculated using Hedges' g, as specified in the following equation, where T is the treatment mean, C is the control mean,  $\delta_{sch}^2$  is the school level variance and  $\delta_{pup}^2$  is the pupil level variance for the null/empty model:

$$ES = \frac{(T-C)_{adjusted}}{\sqrt{\delta_{sch}^2 + \delta_{pup}^2}}$$

The headline effect size will be calculated from the group allocation (intervention/control) coefficient in the full analysis model, with the unconditional variance used as the denominator. The effect sizes will be reported along with confidence intervals and p-values to reflect statistical uncertainty.

#### Longitudinal follow-ups

No longitudinal follow-ups will be undertaken as part of the Reach Evaluation. However, the data will be submitted to the YEF data archive to enable long term follow up by others.

